## 1. PROTOCOL SUMMARY

Title:	Pan-Asia United States PrEvention of Sudden Cardiac Death Catheter Ablation Trial (PAUSE-SCD)
Objective:	

1) To assess the incidence of sudden cardiac death and impact of ablation and ICD therapy vs. ICD therapy alone in Asia, which has not been studied in randomized trials except in the US and Europe.

2) To explore the impact of preemptive VT ablation alone in patients at risk for sudden death (observational registry cohort).

Sample Size:	Pilot study sample size of 120 randomized patients (60 ICD and 60 ICD+ablation). Registry is reserved for patients who refuse randomization and received ablation only.
Design:	Prospective, multi-center randomized, controlled study.
Clinical Sites:	Approximately 8-12 ablation centers in Asia (China, Korea, Japan) will participate in the study. Additional centers may be considered based on the discretion of the principal participating centers. The anticipated enrollment duration is 24 months for the initial pilot enrollment. Additional associated centers may be used for referrals, clinically indicated ICD implantation, NIPS study, and ICD follow up. Due to the COVID19 global pandemic, China centers were shut down and complete access for patient follow-up will require an additional 6-12 months. Therefore, we are requesting one extra year extension for follow up due to these unanticipated circumstances. No statistical review or analysis was performed, as follow-up remains incomplete as of April, 28 th , 2020.
Inclusion Criteria:	

• Patient is receiving a new ICD or CRT-D implant, that has study required programing capabilities and is appropriate for remote monitoring. Patient who has received the ICD / CRT-D within 90 days of enrollment can also be enrolled.

• Patient who has a high risk of ICD shock as shown by documented Monomorphic VT (MMVT) by one or more of the following:

○ Spontaneous MMVT

○ Inducible MMVT during EP Study,

○ Inducible MMVT during NIPS Study

Inducible MMVT is defined as MMVT > 30 seconds or requiring electrical termination ( ATP or cardioversion)

- Patient has EF < 50% or RV dysfunction
- Patient has a cardiomyopathy with structural heart disease of any cause
- 18 years of age or older
- Patient has been informed of the nature of the study and has agreed to its provisions and provided written informed consent approved by the Institutional Review Board.

Exclusion Criteria:

- Any history of debilitating stroke with neurologic deficit
- ST elevation MI or previous cardiac surgery within 60 days prior to enrollment
- Patient is pregnant or nursing
- Patient has chronic NYHA class IV heart failure
- Patient has incessant VT necessitating immediate treatment
- Patient has VT/VF thought to be from channelopathies
- Limited life expectancy (less than one year)
- Patient has current class IV angina
- Recent CABG or PCI (< 45 days)
- Patient is currently participating in another investigational drug or device study
- Patient is unable or unwilling to cooperate with the study procedures
- Known presence of intracardiac thrombi
- Prosthetic mitral or aortic valve or mitral or aortic valvular heart disease requiring immediate surgical intervention
- Major contraindication to anticoagulation therapy or coagulation disorder
- Left Ventricular Ejection Fraction < 15%
- Patient has had a previous ablation procedure for VT, excluding remote (> 3 months) outflow tract tachycardia
- Patient has GFR < 30 mL/min/1.73m^2
- Patient has peripheral vascular disease that precludes LV access
- Patient is thought to have idiopathic outflow VT as only VT
- Patient has a PVC or VT induced cardiomyopathy that is expected to resolve with ablation and will not require an ICD
- Patient has reversible cause of VT
- Patient does not meet criteria for ICD or CRT-D

Intervention:

[figure not shown]
- 1) ICD with medical management
- 2) ICD with catheter ablation. Main strategy is scar-based ablation with targeting of late potentials defined as low voltage potentials with fractionated, split, or delayed components
- 3) Registry on non-randomized patients undergoing ablation only.

Study Endpoint:

The primary endpoint is defined as a composite of recurrent VT, cardiovascular rehospitalization, and death. Prespecified secondary endpoints include each of the individual components of the primary endpoint. Comparison of the ablation-only registry with the randomized patients will serve as an additional secondary outcome measure.

Length of Study:

The trial consists of a 2-3 year recruitment and randomization phase with a 2 year follow-up period. Due to the COVID19 global pandemic, China centers were shut down and complete access for patient follow-up will require an additional 6-12 months. Therefore, we are requesting one extra year extension for follow up due to these unanticipated circumstances. No statistical review or analysis was performed, as follow-up remains incomplete as of April, 28th, 2020.

## 2. INTRODUCTION

### 2.1 Background and Rationale

Sudden cardiac death (SCD) remains the leading cause of death in the United States, totally over 440,000 cases annually. The incidence of SCD in Asia is unknown and the population potentially at risk is over four times the size of the United States. ICD implantation remains the most effective abortive strategy to decrease mortality in the secondary and primary prevention setting. However, the penetration and acceptance of ICD therapy into routine medical practice and guidelines in Asia is incomplete with significant unrealized potential. In 2011, an estimated 800 ICDs were implanted in China, compared to half a million in the United States.

The barriers to widespread adoption of ICD implantation across Asia are multifactorial, including financial, cultural, and scientific factors. In China, the cost of the device is not covered by national insurance, making the technology cost- prohibitive for many

patients who are likely to derive benefit. Cultural biases include aversion to surgery and implantation of devices, in addition to attitudes that reflect culture-specific disease progression. Additionally, the vast majority of scientific evidence and randomized studies that support current ICD guidelines have been performed in US and Europe, outside of Asia. The relative efficacy of ICD therapy in the Asian population has not been formally tested and lack of generalizable data is one factor that impedes widespread adoption among practicing physicians, which has a significant impact on how patients are counseled. Continuity and clinical follow-up are challenges in such vast Asian countries, and the implantation of an ICD offers a potential means of improving upon these limitations. In this current state, Asia serves as the ideal environment and setting to test the efficacy of both ICD therapy and catheter ablation in patients at risk for ventricular arrhythmias and sudden death. Further, mortality impact from both ICD and ablation can be further studied as the majority of patients with structural heart disease referred for VT ablation in Asia do not have an ICD.

ICD therapies have been strongly associated with increased hospitalization and all-cause mortality. As catheter ablation of VT has been demonstrated to decrease recurrent VT and ICD therapies, it is biologically plausible that ablation may have an impact on mortality. A recent multicenter study of 2,061 patients by the International VT Ablation Center Collaboration demonstrated that recurrent VT after catheter ablation was associated with a 7-fold subsequent risk for mortality and across all stages of heart failure, patients that had successful ablation experienced improved survival.(1) Only two randomized studies have been completed to date, SMASH VT (2) and VTACH(3), demonstrating that early preemptive ablation results in statistically significant reduction in subsequent ICD shocks. A trend towards improved survival was seen in the ablation group in SMASH VT.

## 2.2 Study Purpose

The purpose of this study is to demonstrate that scar-based VT ablation in subjects who are clinically indicated for new ICD or CRT-D implantation and are at high risk of ICD shock with spontaneous monomorphic VT or inducible monomorphic VT during EP or NIPS study results in a superior clinical outcome compared to ICD with standard medical therapy. Additionally, the registry arm which will enroll patients that refuse ICD will assess the efficacy of catheter ablation in the absence of background ICD therapy.

Additionally, secondary goals of this study include:

- 1) Increasing SCD awareness in Asia and improving clinical follow-up of patients at risk.
- 2) Assessing whether SCD is less prevalent in Asia than US and Europe and prospectively determine the relative magnitude of benefit of both ICD and ablation.
- 3) Determining the composition and etiology of patients referred for ICD and ablation in Asia. Patients with ischemic cardiomyopathy represent a

disproportionately small proportion of patients referred for VT ablation, despite a high prevalence of coronary artery disease and myocardial infarction. Biological and cultural differences in scar patterns may account for variations in arrhythmogenicity

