#### **3.5.1 Randomization**

Subjects who meet inclusion/exclusion criteria will be entered into the randomized trial. Randomization will be 1:1 between control group and ablation group. Those randomized to the control group will receive ICD therapy and routine drug therapy (including antiarrhythmic drugs as indicated). Subjects randomized to the ablation group will receive ablation therapy plus ICD for ventricular tachycardia. Patients that refuse ICD therapy and undergo ablation only will be enrolled in a prospective registry. All primary statistical analyses will be performed on an intent-to-treat basis.

Central randomization is conducted by the coordinating site. Prior to 10/12/16, the participating sites performed randomization using a table (block size of 4) provided by the coordinating site. After additional in-house statistical review of the protocol, electronic randomization from the coordinating site was advised. Central electronic randomization commenced on 10/12/2016. 25 patients were enrolled using the original randomization table schema. The remaining patients were randomized using electronic randomization.

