#### 3.6.2 Registry Subjects

Patients that refuse ICD implantation will not be randomized and will be approached to sign consent for inclusion into a registry if they undergo catheter ablation without ICD. Basic demographics and medical history will be collected from registry subjects upon enrollment. Registry subjects will receive a phone contact and follow-up with clinic visits and device interrogation at 3, 6, 12, 18, 24, 30 and 36 months to check on their overall status. Due to the COVID19 global pandemic, China centers were shut down and complete access for patient follow-up will require an additional 6-12 months. Therefore, we are requesting one extra year extension for follow up due to these unanticipated circumstances. No statistical review or analysis was performed,

as follow-up remains incomplete as of April, 28th, 2020. Registry subjects will receive a phone contact and follow-up with clinic visits 30 and 36 months to check on their overall status

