### **9.2 Primary Endpoint**

The primary efficacy endpoint is defined as freedom from recurrent VT, cardiovascular rehospitalization, and all-cause mortality through a period of 2 years after the procedure (ablation) or randomization (standard medical therapy). Recurrent VT is defined as any appropriate ICD therapy (shock or ATP) or documented sustained monomorphic VT >30 seconds. Cardiovascular rehospitalization is defined as a hospital admission after the randomized procedure for heart failure, procedure-associated complication, or arrhythmia-related causes during the follow-up period.

Prespecified secondary endpoints include each of the individual components of the primary endpoint. Comparison of the ablation-only registry with the randomized patients will serve as an additional secondary outcome measure.

Prespecified subgroup analysis will be performed for patients with RV cardiomyopathy.

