### **9.3 Primary Endpoint Analysis**

The primary endpoint analysis will be a time to event analysis and account for censored observations for all randomized subjects. Intention to treat analysis will be used for this endpoint; the analysis will be “analyzed as randomized” regardless of the actual treatment patients receive during the follow-up period. Kaplan-Meier (1958) estimates of the primary endpoint and overall survival will be generated along with 95% confidence intervals for the median time to event or death (Brookmeyer and Crowley, 1982).(8,9) Log-rank test will be used to compare the hazard functions between the two groups. Cox (1972) regression models will be fit to assess and adjust for baseline covariates.(10) The median time to VT recurrence as well as the 95% confidence intervals will be reported for both groups. The event free survival probability as well as the 95% confidence intervals at the 24-month follow-up for both groups will be presented. Adverse events will be tabulated by type and level of severity and compared between groups using chi-square or Fisher exact tests.

Secondary analyses comparing outcomes in the ICD+ablation and ICD arms vs. the registry patients (ablation only) will be performed in a similar manner to those described above.

Interim analyses will be generated by the coordinating center annually. A Peto-Haybittle efficacy monitoring boundary will be used: if the p-value for the difference between groups is <0.001, early stopping of the trial will be considered. Using this monitoring bound, the p-value for statistical significance at the final analysis will remain at the nominal 0.05 level.

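### The registry is said to assess the efficacy of ablation without an ICD, but no group has neither ICD nor ablation, so neither planned registry comparison can isolate that effect

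*Combined protocol and SAP*

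**What the plan says.** The plan has three groups. Under 3.5.1, controls receive an ICD with drug therapy, and "Subjects randomized to the ablation group will receive ablation therapy plus ICD for ventricular tachycardia". Under 3.6.2, the third group is a non-randomized registry of people who decline an ICD and have ablation alone. No section describes a group with neither treatment, and none names an external control, historical control or performance goal for the registry.

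The registry's purpose is worded in two ways. The Protocol Summary (section 1) gives it as "To explore the impact of preemptive VT ablation alone in patients at risk for sudden death (observational registry cohort". Section 2.2 goes further: "the registry arm which will enroll patients that refuse ICD will assess the efficacy of catheter ablation in the absence of background ICD therapy". Secondary goal 2 in the same section adds an intention to determine how large the benefit of ICD and of ablation each is.

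On analysis, 9.2 states that "Comparison of the ablation-only registry with the randomized patients will serve as an additional secondary outcome measure", and the Protocol Summary repeats this. Section 9.3 states that "Secondary analyses comparing outcomes in the ICD+ablation and ICD arms vs. the registry patients (ablation only) will be performed in a similar manner" to what precedes it, namely Kaplan-Meier estimates, a log-rank test, and Cox models to assess and adjust for baseline covariates.

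**The concern.** The effect named in 2.2 is that of adding ablation in people who have no ICD. Both comparators in 9.3 have an ICD, so neither supplies the reference group for that effect. Covariate adjustment can reduce differences between the kinds of patient in each group, but it cannot create the missing group. Nor is this a matter of how VT is detected without a device: it would remain with perfect ascertainment, and it applies equally to death.

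Registry membership also depends on having refused an ICD. Section 2.1 lists financial, cultural and scientific barriers to ICD use across Asia, for example "In China, the cost of the device is not covered by national insurance". It is reasonable to suspect that people who decline a device differ in prognosis or follow-up from those who accept one, but that is an inference and not something 2.1 states.

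At stake is how a secondary result is read. A registry p-value set beside the purpose in 2.2 invites a conclusion about ablation alone that the data cannot give.

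**Working it through.** **The plan's own figure.** The only sample size is 120 randomized patients (sections 1, 3.5 and 9.1). With 60 per arm, 50% versus 25% at 2 years and two-sided alpha 0.05, the two-proportion normal approximation gives z = (0.25 × √60 − 1.96 × √(2 × 0.375 × 0.625)) / √(0.25 + 0.1875) = (1.936 − 1.342)/0.661 = 0.90, or 81.6% power. The stated 80% is reproduced. It concerns the randomized arms only. No registry size is given, and the point does not depend on one.

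**Groups by treatment** (3.5.1, 3.6.2):

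| | Ablation | No ablation |
|---|---|---|
| ICD | randomized | randomized |
| No ICD | registry | empty |

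**What each contrast estimates.** Take the empty cell as reference, with hazard 1. Let a be the hazard ratio for ablation without an ICD, i the hazard ratio for an ICD without ablation, x their interaction, and c the selection difference between ICD refusers and randomized patients. The relative hazards are then registry a·c, ICD alone i, and ICD plus ablation a·i·x.

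- Registry versus ICD plus ablation: a·c/(a·i·x) = c/(i·x). The ablation effect cancels.
- Registry versus ICD alone: a·c/i. Ablation is exchanged for the ICD.
- Randomized contrast: a·i·x/i = a·x, the ablation effect with an ICD in place.
- Dividing the second registry contrast by the first: (a·c/i)/(c/(i·x)) = a·x. Using both together only returns the randomized contrast.

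None of these equals a. Perfect adjustment would set c = 1 and still leave 1/(i·x) and a/i. Assuming x = 1 would make a equal to the randomized contrast, but that result owes nothing to the registry.

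**Illustration.** All values are assumed, with x = 1 and c = 1:

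| a | i | Registry / ICD alone | Registry / ICD plus ablation | Randomized |
|---|---|---|---|---|
| 0.5 | 0.5 | 1.0 | 2.0 | 0.5 |
| 1.0 | 0.5 | 2.0 | 2.0 | 1.0 |
| 0.5 | 1.0 | 0.5 | 1.0 | 0.5 |
| 1.0 | 1.0 | 1.0 | 1.0 | 1.0 |

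Rows 1 and 4 give the same registry / ICD ratio although ablation halves the hazard in one and does nothing in the other. Rows 1 and 2 give the same registry / ICD plus ablation ratio for the same reason. With weaker effects, a = i = 0.7 gives 0.7/0.7 = 1.0, and a = 1 with i = 0.7 gives 1/0.7 = 1.43.

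**Selection.** Suppose a prognostic factor with hazard ratio 2 is present in 40% of one group and 20% of the other. Then c is about (1 + 0.4)/(1 + 0.2) = 1.17 if it is commoner in the registry, and 1.2/1.4 = 0.86 if commoner in the randomized arms. The documents do not indicate the direction.

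**The case against.** The strongest reply is that the plan already treats the registry modestly. The Protocol Summary uses exploratory, observational wording. Section 3.1 confines the trial's efficacy objective to ICD plus ablation versus ICD alone. Section 9.2 ranks the registry comparison as an additional secondary measure. All of this stands and limits the weight of the point. It does not remove it: 2.2 still states an efficacy purpose, and the exploratory label is not carried into 9.2 or 9.3.

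Three further replies also stand:

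- A reader might infer that registry versus ICD alone is meaningless and should be dropped. The documents do not support that. It is a legitimate, though confounded, comparison of two strategies, and the other registry contrast is equally self-selected.
- A reader might infer that the plan intends to conclude that ablation alone is as good as an ICD. It does not say so. Section 9.3 speaks only of comparing outcomes and sets no equivalence or non-inferiority hypothesis, margin or decision rule for the registry.
- A reader might infer that no adjustment is planned. The Cox models in 9.3 may well carry over to the registry, but so does the unadjusted log-rank test, and nothing specific to ICD refusal is described.

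**Conclusion.** The point holds in limited form. The purpose stated in 2.2 is not identified by either comparison in 9.3, because the group with neither treatment is empty and nothing external replaces it. This follows from the group definitions alone and needs no numerical assumption. The hazard ratios above are assumed; they show that masking is possible, not how large it would be here.

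The fault lies in the efficacy wording of 2.2 and in the analysis and interpretation of the registry contrasts in 9.3. It affects one secondary aim. Two stronger conclusions are not supported: that the randomized result is compromised, since its sample size, primary analysis and interpretation are untouched; and that 2.1 shows cost or culture to bias prognosis, since it lists barriers to ICD adoption and makes no such link. The change is worth making because it alters what the trial may claim from the registry.

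**What to change.** - **Section 2.2:** replace the efficacy wording with *will describe outcomes after catheter ablation in patients who refuse an ICD*, in line with the Protocol Summary. Limit secondary goal 2 so that it claims no separate ICD benefit from registry data.
- **Section 9.3:** report 24-month event-free survival and overall survival for the registry with 95% confidence intervals. Keep both registry contrasts if wanted, but as exploratory, covariate-adjusted estimates with confidence intervals in place of an unadjusted log-rank test. Use the baseline data already collected (3.6.2 provides for basic demographics and medical history). Label one contrast as no ICD versus ICD among ablated patients, and the other as ablation without ICD versus ICD without ablation. State that neither supports an efficacy or equivalence claim.
- **Section 9.2 and the Protocol Summary:** make the same change to the sentence on the registry comparison.

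This needs no new data and leaves the randomized analysis as it is. The documents state that no analysis had been performed as of 28 April 2020, so in this version the change precedes results. The cost is one secondary efficacy claim and any confirmatory reading of the registry p-values.

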### **3. STUDY DESIGN**

#### **3.1 Study Objective**

The study is a prospective, multi-center, randomized controlled trial evaluating the efficacy of ICD plus catheter ablation vs. ICD alone in preventing recurrent VT, cardiovascular rehospitalization, and death in patients with primary and secondary indications for ICD implantation.

#### **3.2 Study endpoints**

The primary efficacy endpoint is defined as freedom from recurrent VT, cardiovascular rehospitalization, and all-cause mortality through a period of 2 years after the procedure (ablation) or randomization (standard medical therapy). Recurrent VT is defined as any appropriate ICD therapy (shock or ATP) or documented sustained monomorphic VT >30 seconds. Cardiovascular rehospitalization is defined as a hospital admission after the randomized procedure for heart failure, procedure-associated complication, or arrhythmia-related causes during the follow-up period.

#### **3.3 Clinical Centers**

We anticipate enrollment of 120 patients for this pilot study at 8-12 institutions with extensive experience in complex ablation procedures. As a conservative estimate, enrollment will occur over a 2 year period, with 60 patients per year (7-8 patients/year at each institution). Additional centers may be considered based on clinical competency and experience.

